In the event a patient with prior use of biologic treatment, systemic steroids or immunomodulating treatments is enrolled, past medical records are required to document when these treatments were stopped. All concomitant or rescue therapies will be recorded (including time of intake and dose on study days) on the appropriate pages of the CRF.

Restrictions regarding concomitant treatment during the trial

Topical treatment

Topical treatment for PPP is not allowed throughout the study. Topical treatment for other conditions is not restricted, however, the patient should avoid applying it with bare hands (e.g. use gloves) when the topical treatment is applied on affected body areas.

Topical corticosteroids

Topical corticosteroids for the treatment of PPP are not allowed during the trial unless they are needed as rescue therapy. Topical corticosteroids for body area other than palms and soles are allowed. The dose and mode of administration should be kept unchanged, if possible. The patient should avoid applying it with bare hands (e.g. use gloves).

Systemic immunomodulating treatments

Systemic corticosteroids and other immunomodulating agents (such as methotrexate, fumaric acid acitretin, ciclosporin, apremilast) for the treatment of PPP are not allowed unless they are needed as rescue therapy.

Biologic treatment

Biologic treatment is not allowed throughout the study, unless it is needed as rescue therapy.

Non-steroidal anti-inflammatory drugs (NSAIDs)

The use of NSAIDs is allowed, however it is recommended that a stable dose is maintained and the drug is not changed throughout the study up to at least the primary endpoint at Week 16.

Rescue therapy for the treatment of worsening of PPP

Rescue therapy is defined as both the use of medication such as topical corticosteroids or other topical treatment applied on the palms and/or soles, systemic immunomodulating treatments or biologics and therapy such as tonsillectomy, for the treatment of worsening of PPP.

The use of the rescue therapy leads to the discontinuation of the trial treatment, but the patient should remain in the trial observation.

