7.3 HANDLING OF MISSING DATA

For the primary efficacy endpoint which is continuous in nature, the use of a restricted maximum likelihood (REML)-based mixed model repeated measures (MMRM) approach, in the primary analysis, will ensure that missing data are handled implicitly, via a missing at random assumption, by the statistical model.

In order to check the robustness of the primary MCPMod analysis to missing data, a sensitivity analysis will be performed using adjusted multiple imputation. Non-monotone missing data will initially be multiply imputed as missing-at-random. For monotone missing data, a Jump to Reference method will then be implemented via a sequential regression MI approach. For such missing data, patients in the active treatment groups are assumed to lose any treatment effect with their missing observations and to then assume a trajectory similar to that of the placebo group. For each imputed complete dataset, an ANCOVA (Analysis of Covariance) model for Week 16 data analogous to the primary MMRM model will be used for the analysis. The results will be pooled using Rubin's rules and the primary MCPMod analysis will be repeated on the summarized outcomes. Further details on the procedure will be included in the TSAP.

For secondary efficacy endpoints of a binary nature, a Non Response Imputation (NRI) approach, will be applied to the missing visits up to Week 52 that is, imputing as a failure to achieve a response in the visits with missing endpoint score, however:

- If there are available data at the visits both before and after the visit with a missing outcome, then impute as a success only if both the preceding and the following measurement indicate success (that is, score of 1) and there is no use of rescue therapy for disease worsening within this imputation period;
- Otherwise, impute as a failure to achieve a response (i.e. no response imputation).

Multiple imputation will be used as a sensitivity analysis to handle missing secondary binary data. Detailed description of multiple imputation will be included in the TSAP.

With respect to safety evaluations, it is not planned to impute missing values.

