[Table 6.3: 1](#) illustrates the data sets which are to be used for each category class of endpoints, and the approaches used with regard to missing data. For explanation of the different methods of handling missing data, cf. [Section 6.6](#).

Table 6.3: 1 Patient sets analysed

Class of endpoint	Patient set					
	ES	RS	SAF (including SAF-post 16)	FAS (including FAS-post 16, m-FAS)	PPS	█
Disposition	OR	OR				
Compliance and exposure			OR			
iPD		OR				
Demographic/baseline characteristics			OR	OR		
CM			OR			
Primary efficacy endpoint				EC-MMRM, EC-MMRM ¹ EC-EP-MMRM ¹ EC-E19-MMRM ¹ EC-ID-MMRM ¹ EC-MI ¹ , OC ² , OC-IR ²	EC-MMRM ¹	
Secondary efficacy endpoints (Binary)				EC-NRI, EC-NRI ^{1,3} EC-EP-NRI ^{1,3} EC-E19-NRI ^{1,3} EC-ID-NRI ^{1,3} EC-BRI ^{1,3} OC ² , OC-IR ²		
Secondary efficacy endpoints (Continuous)				EC-MMRM, EC-MMRM ^{1,3} OC ² , OC-IR ²		
	█	ADA/Nab				OR

¹ sensitivity analysis or subgroup analysis
² descriptive display only
³ selected endpoints.

EC: Primary estimand for binary and continuous efficacy endpoints. Any data collected after use of any rescue therapy or after 6 weeks following last drug administration if patient early discontinued treatment (to allow for incorporation of the continuing maximum treatment effect period) are censored.

[figure not shown]
EC-EP: Alternative estimand for binary and continuous efficacy endpoints. Any data collected after use of any rescue therapy or restricted therapy for other purpose or after 6 weeks following last drug administration if patient early discontinued treatment (to allow for incorporation of the continuing maximum treatment effect period) are censored.

[figure not shown]
EC-E19: Alternative estimand for binary and continuous efficacy endpoints. Any data collected after use of any rescue therapy or after the first visit with missing treatment due to COVID-19 or after 6 weeks following last treatment before or at discontinuation (to allow for incorporation of the continuing maximum treatment effect period) are censored.

EC-ID: Alternative estimand for binary and continuous efficacy endpoints. Any data collected after use of any rescue therapy are censored.

"NRI", "MMRM" and "MI" represent analyses involving imputed data, cf. [Section 6.6.2](#).

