For all binary endpoints (i.e. endpoints that are either 1 (patient responded) or 0 (patient did not respond)), the following will be performed as the primary imputation approach (analysis type: No Response Imputation [NRI]):

- If there are data at visits both before and after the visit with a missing outcome, then impute as success only if both neighbouring visits also represent a success (independent of whether the preceding and following observations were selected for analysis based on time windows described in [Section 6.7](#) and no rescue treatment has been given during this period);
- Otherwise, impute as a failure to achieve a response

Other imputation scheme will be also considered for analysis of the secondary binary efficacy endpoints.

- Best response imputation (BRI): impute all missing values based on the best response observed for the patient at visits prior to withdrawal/occurrence of missing data (independent of whether the observations were selected for analysis based on time windows described in [Section 6.7](#)). If there is no non-missing data available (including baseline), then the missing value will be imputed as a failure.

OC and OC-IR methods will be also used to display the binary data.

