Assignment of observations to visits based on time windows will be based on the non-imputed (observed) data after the implement of estimand concepts. For example, for EC and OC methods, values after rescue therapy intake or 6 weeks following last treatment in case of discontinuation should be censored first before assignment of efficacy endpoints..

For visits without an assigned value based on time windows, a value will thereafter be imputed as defined in [Section 6.6](#). Imputation of efficacy endpoints, when applicable, will be performed based on all available observations meeting the imputation rules, irrespective of whether the observation was selected in any time window.

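### EC-BRI codes a patient rescued for worsening PPP before Week 16 as a Week 16 responder if any earlier visit showed response

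*SAP*

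**What the plan says.** - **BRI (SAP 6.6.2, binary endpoints).** The rule is to "impute all missing values based on the best response observed for the patient at visits prior to withdrawal/occurrence of missing data". It has no condition about rescue.
- **NRI (SAP 6.6.2, the main rule).** A gap is filled as a success only if the visits on both sides are successes and "no rescue treatment has been given during this period". In every other case it is a failure. Protocol 7.3 sets the same condition, allowing an imputed success only where "there is no use of rescue therapy for disease worsening within this imputation period".
- **EC (notes to SAP Table 6.3: 1).** It is the "Primary estimand for binary and continuous efficacy endpoints. Any data collected after use of any rescue therapy" is removed, as are data from more than 6 weeks after the last dose in patients who stop treatment early.
- **Order of steps (SAP 6.7).** First, "values after rescue therapy intake or 6 weeks following last treatment in case of discontinuation should be censored first before assignment of efficacy endpoints". Then, "For visits without an assigned value based on time windows, a value will thereafter be imputed as defined in" Section 6.6.
- **Rescue (Protocol 4.2.2.1).** Under "Rescue therapy for the treatment of worsening of PPP", the definition covers topical treatment of palms or soles and "systemic immunomodulating treatments or biologics and therapy such as tonsillectomy, for the treatment of worsening of PPP". Taking it ends trial treatment.
- **Status of EC-BRI (SAP Table 6.3: 1).** It is footnoted as a sensitivity or subgroup analysis for selected binary secondary endpoints.

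**The concern.** The two binary imputation rules treat rescue in opposite ways. NRI, and Protocol 7.3 behind it, will not fill in a success across a period that contains rescue. BRI looks only at earlier results, so once EC has removed the post-rescue data it can turn a rescued patient into a responder. It does so even when the last value before rescue was a non-response.

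A sensitivity analysis of PPP ASI50, PPP ASI75 or PPP PGA response is meant to show how far the result depends on values that are missing. If some gaps come from rescue for worsening disease and are filled with success, part of any gap between EC-BRI and EC-NRI reflects that coding and not uncertainty about missing data.

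**Working it through.** No sample size, power or alpha in the documents depends on this rule, so there is no planned figure to reproduce. The check is a trace of the rules in the order SAP 6.7 gives, followed by simple arithmetic.

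**Trace at Week 16 (PPP ASI50; 1 = response, 0 = none)**

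| Hypothetical patient | Week 16 after EC | NRI | BRI as written | BRI with rescue condition |
|---|---|---|---|---|
| A: response at Week 8, none at Week 12, rescue before Week 16 | censored | 0 | 1 | 0 |
| B: never a response, rescue before Week 16 | censored | 0 | 0 | 0 |
| C: response at Weeks 8 and 12, Week 16 visit missed, no rescue, no later value | missing | 0 | 1 | 1 |
| D: last dose at Week 12, no rescue, Week 16 assessed | observed | observed | observed | observed |

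In A, the pre-rescue values at Weeks 1, 2, 3, 4, 8 and 12 are 0, 0, 0, 0, 1, 0. The best is 1, so BRI returns 1. NRI finds no usable value after the gap and returns 0. In D, Week 16 falls 16 − 12 = 4 weeks after the last dose. That is inside the 6 weeks EC retains, so no imputation rule applies.

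**Effect per patient**

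Arm sizes are 40/20/20/20/40 (Protocol synopsis). The shift in the EC-BRI rate is 100 × k / n for k patients like A in an arm of n:

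- n = 20: k = 1, 2, 3 gives 5, 10, 15 points
- n = 40: k = 1, 2, 3 gives 2.5, 5, 7.5 points

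**Effect under assumed rates**

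The documents give neither the share r rescued before Week 16 nor the share q of those with an earlier response. As assumptions only, take r from 5% to 20% and q from 25% to 50%. The shift in one arm is r × q:

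- lowest: 0.05 × 0.25 = 1.25 points
- highest: 0.20 × 0.50 = 10 points

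With the same q in both arms, the shift in active minus placebo is (r active − r placebo) × q:

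- (0.20 − 0.05) × 0.50 = +7.5 points
- (0.05 − 0.20) × 0.50 = −7.5 points

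The sign stays open even if active patients are likelier to have responded earlier. Take q = 50% on active and 25% on placebo:

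- r = 10% in both arms: 5 − 2.5 = +2.5 points
- r = 10% active, 20% placebo: 5 − 5 = 0 points
- r = 5% active, 20% placebo: 2.5 − 5 = −2.5 points

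**The case against.** **Nothing decisive depends on EC-BRI.** This stands. Proof of concept rests on the continuous primary endpoint, SAP 5.2.1 names no key secondary endpoint, and the main binary analysis already scores patient A as a failure.

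**BRI may be a deliberate optimistic contrast to NRI.** This is possible, since the SAP states no purpose for it. The fix does narrow that contrast. But optimism about a missed visit (patient C) is different from coding success after an observed loss of response and rescue for worsening (patient A).

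**Under the plan's estimand the outcome after rescue is unobserved, not a known failure.** This limits the wording. Protocol 2.1.1 describes the primary comparison as setting aside the effects of discontinuation and rescue, and the same censoring applies to the secondary endpoints. BRI still does not estimate what would have happened without rescue: it passes over the latest result in favour of a better, older one. For binary endpoints the plan's own NRI in effect treats rescue as failure.

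**Other views of the data exist.** This stands. OC and OC-IR displays are planned, and OC-IR includes values after rescue. Protocol 7.3 names multiple imputation as the binary sensitivity analysis, and SAP 4 does not list dropping it as a change, although the visible SAP 6.6.2 describes only BRI besides NRI.

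A reader might also infer three stronger points that the documents do not support:

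- *The rule tilts the comparison towards the drug.* That needs rescue rates by arm, which are not given; more rescue on placebo would cancel or reverse it.
- *Any difference between EC-BRI and EC-NRI is only miscoding.* BRI also fills gaps from other causes, such as visits missed because of COVID-19.
- *Patients who stop for lack of efficacy should be set to non-response at Week 16 as well.* EC keeps data for 6 weeks after the last dose, so this would overwrite valid observed values such as patient D's, making BRI stricter than NRI for them.

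**Conclusion.** The rule as written produces a code that conflicts with the plan's own handling of rescue: a patient rescued for worsening PPP before Week 16 becomes an EC-BRI responder if any earlier visit showed response, even when loss of response was recorded before rescue. This follows from reading SAP 6.3, 6.6.2 and 6.7 together and needs no assumption. No visible text sets such patients to non-response under BRI.

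The scope is narrow. Only patients whose Week 16 value is censored for rescue and who had an earlier response are affected, and only in a supplementary analysis of selected endpoints. Each one moves the rate by 5 points in a 20-patient arm or 2.5 points in a 40-patient arm. Any total, and the sign of the effect on the treatment difference, depends on rescue and earlier-response rates that the documents do not give. The correction is worth making because it is cheap and removes an internal inconsistency; the trial's main conclusions are not at risk.

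**What to change.** In SAP 6.6.2, add NRI's rescue condition to BRI: visits whose values are censored because of rescue therapy are imputed as non-response, and best response is carried forward only into values missing for other reasons. Leave observed values within 6 weeks after the last dose as they are, and add no override for patients who stop for lack of efficacy.

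This is one sentence and a small programming change; rescue use is already recorded on the CRF (Protocol 4.2.2.1). EC-BRI response rates become slightly lower, and BRI becomes a less extreme optimistic contrast to NRI. EC-NRI and primary endpoint results do not change.

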6.6.3 Safety data

With respect to safety evaluations, it is not planned to impute missing values. For safety data that are displayed by time point (or visit) of measurement, the OC-IR approach will be used. For safety data that are not displayed by visit such as AE and possibly clinically significant laboratory abnormality, OR will be used.

The only exceptions where imputation might be necessary for safety evaluation are AE dates and start and stop dates for concomitant medications. Missing or incomplete AE dates are imputed according to BI standards (4).

Partial start and stop dates for concomitant medications, rescue, and historical medication for PPP will be imputed to enable subsequent calculation (but not for display) by the following "worst case" approach:

- If the day of the end date is missing, then the end date is set to last day of the month (or to the patient's trial completion date, if it is earlier than the last day of the month).
- If the day and month of the end date are missing then the end date is set to 31st of December of the year (or to the patient's trial completion date, if it is earlier than the 31st of December of the year).
- If the day of the start date is missing the start date is set to first day of the month (except for rescue therapy, where the first dosing day will be used if first dosing happened in the same month).
- If the day and month of the start date are missing then the start date is set to 1st January of the year (except for rescue therapy, where the first dosing day/month of study medication will be used if first dosing happened in the same year).
- All other cases need to be assessed by the trial team on an individual basis, using the above points as guidance.

If a concomitant medication was ticked to be ongoing, it is expected that the end date is missing and will not be imputed for display purposes.

6.6.7 Time since first diagnosis/tonsillectomy

For incomplete information on the date of first diagnosis, time since first diagnosis will be calculated as follows:

- If the year of first diagnosis is unknown, time since first diagnosis will be set to missing.
- If day and month of the first diagnosis are unknown, time since first diagnosis will be calculated as if diagnosed on the 30th June of that year.
If only the day of the first diagnosis is unknown, time since first diagnosis will be calculated as if diagnosed on the 15th of that month.

Time since tonsillectomy will be imputed in the same way.

6.7 BASELINE, TIME WINDOWS AND CALCULATED VISITS

Measurements reported with date and time and taken prior to start of administration of trial treatment will be considered pre-treatment values. Measurements reported with a date only (and no time) and taken on the day of first administration of trial treatment will also be considered pre-treatment values. These pre-treatment values will be assigned to visits according to the nominal visit number as recorded on the eCRF or as provided by the laboratory.

Baseline, unless otherwise specified, is defined as the last measurement collected prior to the start of administration of the trial treatment.

Measurements taken after start of administration of trial treatment will be considered either on- or off-treatment values based on the definition in [Section 6.1](#), and will be assigned to visits for statistical analysis, if applicable, as defined below.

Analysis of AE data, potentially clinically significant abnormal laboratory values, concomitant medication or non-drug therapies, as well as use of rescue therapy will not be based on visits. Frequency tables for these data will be using on-treatment data and categorized based on their occurring/starting dates. Therefore, no assignment to time windows will be necessary for such data.

The derivation of the last value, minimum value and maximum value of laboratory and vital signs data will consider all on-treatment values (whether or not selected in any time window; see [Table 6.1: 1](#) for definition of the on-treatment period) within the period of interest; these will be derived for analysis of laboratory and vital signs data.

All other safety, efficacy XXXXXXXXXX measurements will be assigned to visits based on extended time windows around the planned visit dates, defined relative to the day of first trial

treatment (which is scheduled for Visit V2). These extended time windows are defined in [Table 6.7: 1](#).

Table 6.7: 1 Time windows for assignment of efficacy, safety lab, vital XXXXXXXXXX measurements to visits for statistical analysis

Visit number / name	Visit label	Planned day	Time window (Days)				
			Window (per CTP)	Start (per CTP)	End (per CTP)	Start (extended)	End (extended)
V1	Screening	- 28 to - 14					
V2	Day 1	Day 1		1 ^A	1	1 ^A	1
V3	Week 1	Day 8	+/- 2	6	10	2	11
V4	Week 2	Day 15	+/- 2	13	17	12	18
V5	Week 3	Day 22	+/- 2	20	24	19	25
V6	Week 4	Day 29	+/- 2	27	31	26	43
V7	Week 8	Day 57	+/- 7	50	64	44	71
V8 ^C	Week 12	Day 85	+/- 7	78	92	72	99
V9	Week 16	Day 113	+/- 7	106	120	100	127
V10	Week 20	Day 141	+/- 7	134	148	128	155
V11	Week 24	Day 169	+/- 7	162	176	156	183
V12	Week 28	Day 197	+/- 7	192	204	184	211
V13	Week 32	Day 225	+/- 7	218	232	212	239
V14	Week 36	Day 253	+/- 7	246	260	240	267
V15	Week 40	Day 281	+/- 7	274	288	268	295
V16 ^C	Week 44	Day 309	+/- 7	302	316	296	323
V17	Week 48	Day 337	+/- 7	330	344	324	351
V18 ^D	Week 52 (EoT)	Day 365	+/- 7	358	372	352	393
V19	Week 60	Day 421	+/- 7	414	428	394	449
V20	Week 68 (EoS)	Day 477	+/- 7	470	484	450	491

For patients who discontinue the treatment early and are not willing to follow the whole visit schedule:

- EoS LD^B+112 - - -

Days are counted relative to the day of first treatment, which is defined as Day 1.

^A Note that measurements made at Day 1 and assigned to the on-treatment period (because mistakenly made after start of infusion of trial treatment) via assessment on date and time (i.e. safety laboratory) will not be assigned to Day 1. Such data will be listed only.

^B LD=Last dose.

^C Data within the extended time window of Week 8/16 but after the actual dose at Week 8/16 will not be selected to represent Week 8/16 except for local tolerability and post-dose vital sign assessments.

^D For the patients who enter OLE trial, the EOT will be the last visit (i.e., V19 and V20 are not required). The EOS (=individual end of the study) will be the first administration of the trial drug in OLE trial.

Repeated and unscheduled efficacy, safety XXXXXXXXXX measurements will be handled similarly to scheduled measurements and will also be assigned to a time window depending upon the date of measurement.

Only one observation per time window will be selected for statistical analysis at a particular visit – the value which is closest to the protocol planned visit day will be selected. If there are two observations which have the same difference in days to the planned day, the later value

will be selected. If there are two observations on the same day, the worst value will be selected.

Note that data within the extended time window of Week 8/16 but after the actual dose at Week 8/16 will not be selected to represent Week 8/16 except for local tolerability and post-dose vital sign assessments.

Assignment of observations to visits based on time windows will be based on the non-imputed (observed) data after the implement of estimand concepts. For example, for EC and OC methods, values after rescue therapy intake or 6 weeks following last treatment in case of discontinuation should be censored first before assignment of efficacy endpoints..

For visits without an assigned value based on time windows, a value will thereafter be imputed as defined in [Section 6.6](#). Imputation of efficacy endpoints, when applicable, will be performed based on all available observations meeting the imputation rules, irrespective of whether the observation was selected in any time window.

